NOTES: Actual study visit procedures can be done \pm 3 days of the targeted visit date. Clinical response assessment is based on physical examination and blood sample. Spleen and lymph node measurements will be performed during the physical examination or via ultrasound for clinical response assessment. If clinical response assessment is suggestive of a CR/CRi, a CT will be taken for confirmation of the clinical response. If a CT scan indicates a CR/CRi, a bone marrow biopsy will be required as soon as possible to confirm the clinical response (the sample will be split for analyses of disease and biomarker assessments). The CT scan and bone marrow biopsy will have a \pm 7-day window. Venetoclax and ibrutinib dosing occurs once daily until end of treatment. Blood samples for optional biomarker assessments will be collected for subjects who provided consent for the correlative studies. Bone marrow sample for optional biomarker assessments to be collected for subjects who provided consent for the relative studies AND if a bone marrow sample is collected to confirm CR/CRi or collected per standard-of-care. Urine pregnancy test will be performed every 4 weeks for women of childbearing potential; testing will be performed at home in between site visits.

Final Visit:

	INTERVIEW	Adverse event assessment Concomitant therapy Eastern Cooperative Oncology Group performance assessment	Dispense/collect subject calendars/diaries and dosing instructions
	EXAMINATION	Physical examination Vital signs	Weight Clinical response assessment
	LABORATORY	Hematology/chemistry sample Computed tomography (if needed for confirmation of CR/CRi) Bone marrow sample (if needed for confirmation of CR/CRi)	Urine pregnancy test Blood sample for optional biomarker assessments

NOTES: The final visit will occur at the end of study treatment. Actual study visit procedures can be done within 7 days before the targeted visit date. Clinical response assessment is based on physical examination and blood sample. If clinical response assessment is suggestive of a CR/CRi, a CT will be taken for confirmation of the clinical response. If a CT scan indicates a CR/CRi, a bone marrow biopsy will be required as soon as possible to confirm the clinical response (the sample will be split for analyses of disease and biomarker assessments). Blood samples will be collected for optional biomarker assessments for subjects who provided consent for the correlative studies. Bone marrow sample for optional biomarker assessments to be collected for subjects who provided consent for the relative studies AND if a bone marrow sample is collected to confirm CR/CRi or collected per standard-of-care.

2.2 Individual Post-Treatment Period Visit Activities

This section presents a list of activities performed during each visit, organized by visit. The dot pattern on the upper right indicates the place of the visit in the overall post-treatment period activity schedule.

Activities are grouped by category (interview, examination, etc.). Further information about the activities is presented in Section 3.

30-Day Follow-Up Visit:

 INTERVIEW	Adverse event assessment	Concomitant therapy
 EXAMINATION	Physical examination Weight	Vital signs
 LABORATORY	Hematology/chemistry sample	Urine pregnancy test

NOTES: Follow-up visit to be conducted no earlier than 30 days after the last dose of study drug (venetoclax or ibrutinib) but prior to any new anticancer therapy. A symptom-directed physical examination will be performed at the follow-up visit. Urine pregnancy testing to be performed every 4 weeks up to 30 days after the last dose of venetoclax and 90 days after the last dose of ibrutinib, whichever the latest.

Post-Treatment Follow-Up Visits:

 INTERVIEW	Adverse event assessment	Concomitant therapy
 EXAMINATION	Physical examination Weight Physical examination (or ultrasound) of lymph nodes and spleen	Vital signs Clinical response assessment
 LABORATORY	Hematology/chemistry sample Computed tomography (if needed for confirmation of CR/CRi)	Bone marrow sample (if needed for confirmation of CR/CRi) Blood sample for optional biomarker assessments

NOTES: Post-treatment follow-up visits will be conducted until documented progressive disease (PD) or other post-treatment therapies (including stem cell transplantation) are received. The post-treatment follow-up visits will follow the same schedule as the visit schedule (i.e., Week 4, Week 8, Week 12, Week 16, Week 24, Week 36, and every 12 weeks thereafter).

Clinical response assessment is based on physical examination (or ultrasound) and blood sample.

Spleen and lymph node measurements will be performed during the physical examination or via ultrasound.

If clinical response assessment is suggestive of a CR/CRi, a CT will be taken for confirmation of the clinical response. If a CT scan indicates a CR/CRi, a bone marrow biopsy will be required as soon as possible to confirm the clinical response (the sample will be split for analyses of disease and biomarker assessments).

Blood samples will be collected for optional biomarker assessments for subjects who provided consent for the correlative studies.

Bone marrow sample for optional biomarker assessments to be collected for subjects who provided consent for the relative studies AND if a bone marrow sample is collected to confirm CR/CRi or collected per standard-of-care.

Survival Follow-Up:

 INTERVIEW	Survival assessment	Any new anticancer therapy
---	---------------------	----------------------------

NOTES: Subjects who discontinue the study drug and are no longer in post-treatment follow-up should be contacted every 6 months by telephone for survival assessment and for information on new anticancer therapies.

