	
requires treatment and suitable for oral administration of study drugs. Subjects should meet the following disease activity criteria: an Eastern Cooperative Oncology Group performance status ≤ 2.
 
Subjects should have laboratory values meeting the following criteria:
 
 alanine aminotransferase/aspartate aminotransferase $\leq 3 \times$ the upper limit of normal (ULN); adequate liver function as indicated by a total bilirubin $\leq 1.5 \times$ ULN (subjects with documented Gilbert's syndrome may have bilirubin $> 1.5 \times$ ULN); absolute neutrophil count $> 1000/\mu\text{L}$; platelet count $> 50,000/\mu\text{L}$; creatinine clearance ≥ 50 mL/minute; and hemoglobin > 8 g/dL.

Study Drug and Duration of Treatment:
	
Ibrutinib 420 mg will be dosed orally (PO), once daily (QD) starting on Day -1.
 
Venetoclax will be initiated on Week 1, Day 1 with an initial 5-day dose ramp-up for venetoclax. Venetoclax 400 mg (target dose) will be dosed PO, QD; an option to increase the dose of venetoclax to 600 mg QD will be available at Week 8 or thereafter if there is evidence of incomplete response and/or if the dose of ibrutinib has been decreased to 280 mg/day or 140 mg/day due to toxicity management. The dose of venetoclax should not be increased to 600 mg/day in subjects with significant venetoclax toxicity. The maximum dose allowed for venetoclax is 600 mg/day.
 
Treatment duration of combination treatment will be as follows:
 
 eligible subjects will proceed to stem cell transplantation after reaching complete remission (CR) (combination therapy will be discontinued but subjects will be followed for disease progression) 2 years, will be given to subjects who are ineligible for stem cell transplantation unless treatment is intolerable or the subject develops progressive disease 
For subjects who continue to derive clinical benefit after 2 years of treatment, AbbVie will work with the investigator to consider the potential continuation of therapy, as per local regulations.

Date of Protocol Synopsis:
	
11 November 2020

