3.11 Post-Treatment Follow-Up and Survival Visits

Subjects who discontinue study drug but have not experienced progressive disease (PD) will return for post-treatment follow-up visits. The post-treatment follow-up visits will follow the same schedule as the visit schedule (i.e., Week 4, Week 8, Week 12, Week 16, Week 24, Week 36, and every 12 weeks thereafter). Subjects will return for post-treatment follow-up visits until study completion starting from study drug discontinuation until documented PD or other post-treatment therapies (including stem cell transplantation) are received. Follow-up hematology and disease response assessment data will be collected.

Survival information (i.e., the date and cause of death) will be collected via telephone calls at 6-month intervals or as needed to allow for more frequent survival analyses.

All subjects will be followed for survival information (i.e., date and cause of death, all poststudy anticancer treatment including stem cell transplantation, reasons for poststudy anticancer treatment, regimens, dates of initiation and completion, etc.) unless the subject requests to be withdrawn from the

study survival follow-up; this request must be documented in the subject's medical record and signed by the investigator. If the subject withdraws from study follow-up, the study staff may use a public information source (such as county records) to obtain information about survival status only, as appropriate per local regulations.

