3.14 Disease Assessment

All measurable disease must be documented at screening (baseline) before the first dose of study drug for all subjects based on the analysis of clinical laboratory tests (hematology), physical examination, and contrast-enhanced CT scan of involved neck, chest, abdomen, and pelvis (or MRI, if CT scan is medically contraindicated).

For all subjects, clinical response (laboratory and physical examination assessments) will be assessed by the investigator during Weeks 4, 8, 12, 16, 24, 36 and every 12 weeks thereafter, and at the final visit. Note: disease assessments may be performed approximately 7 days before the scheduled visit. The clinical response will be assessed by laboratory tests and physical examination (or ultrasound) using the T-PLL consensus criteria¹ (as outlined in [Table 2](#)).

If clinical response is suggestive of a CR/CRi, a CT scan with contrast (or MRI) should be done for a confirmatory assessment as outlined in [Section 3.13](#).

If a CT scan indicates a CR/CRi, a bone marrow aspirate and biopsy will be required as soon as possible to confirm the clinical response. For subjects who opt-in for correlative biomarker analyses, a portion of the bone marrow aspirate should be split for the optional biomarker collections listed in [Section 3.17](#).

To meet the CR criteria, the CT scan and bone marrow are both required to be negative. Some subjects fulfill all the criteria for a CR but have a persistent anemia, thrombocytopenia, or neutropenia apparently unrelated to T-PLL, but related to drug toxicity. These subjects will be assessed with a response of CRi.

Disease assessment will continue to be performed after the last dose of study drug until disease progression for any subject who has not experienced PD at the time of permanent discontinuation of venetoclax and ibrutinib.

Table 2. Clinical Response Criteria (Based on Physical Examination/Ultrasound and Laboratory Tests)

Group	Parameter	Complete Remission (all met)	Partial Remission (≥ 2 in Group A and ≥ 1 in B met)	Stable Disease (all met)	Progressive Disease (≥ 1 in Group A or B met)
A	Lymph nodes by physical examination/ultrasound	All long-axis diameters to < 1.0 cm	Decrease $\geq 30\%$ in SLD	Change of -29% to $+20\%$ in SLD	Increase in $> 20\%$ in SLD from Nadir ^a

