Parameter	Sample ^{a,b} (volume)	Day –28 through Day –2	Week 1 (Day –1, Day 1, Day 6)	Weeks 4, 8, 12, 16, and 24	Week 36 and Every 12 Weeks Thereafter	Final Visit ^c and PTFU ^d
MRD (molecular)	Peripheral blood (6 mL)	X		X	X	X
Tumor profiling	Peripheral blood (8 mL)	X				
Tumor ex vivo sensitivity	Peripheral blood (8 mL)	X	X ^e			
MRD (molecular)	Bone marrow (2 mL)			Any time during the study (i.e., confirmation of a clinical response).		
Tumor profiling	Bone marrow (1 mL)			Any time during the study (i.e., confirmation of a clinical response).		
Tumor ex vivo sensitivity	Bone marrow (3 mL)			Any time during the study (i.e., confirmation of a clinical response).		
Germline control for tumor profiling	Cheek swab	X				

MRD = minimal residual disease; PTFU = post-treatment follow-up

- Peripheral blood for biomarker assessment will be taken at indicated time points and any other time during the study with a bone marrow sample for confirmation of a clinical response.
- If a computed tomography scan indicates a CR/CRi, a bone marrow sample will be taken during the study to confirm the clinical response; the sample will be split for analyses of disease and biomarker assessments provided informed consent was given for correlative studies.
- The final visit will occur at the end of the study or the end of study treatment.
- Post-treatment follow-up visits will be conducted until documented progressive disease or other post-treatment therapies (including stem cell transplantation) are received. The post-treatment follow-up visits will follow the same schedule as the visit schedule (i.e., Week 4, Week 8, Week 12, Week 16, Week 24, Week 36, and every 12 weeks thereafter).
- Predose and 6 hours post-venetoclax dose.

Note: Participation in the biomarker/correlative studies is optional. If informed consent is provided, then peripheral blood and/or bone marrow biospecimens will be collected at the indicated time points.

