6.3 Secondary Efficacy Analysis

The secondary efficacy analysis will be performed for the following endpoints:

Progression-Free Survival (PFS) will be defined as the number of days from the date of first dose of study drug to the date of earliest disease progression or death. All events of disease progression will be included regardless whether the event occurred while the subject was taking the study drug or had previously discontinued the study drug. If the subject has not experienced disease progression or death, the subject's data will be censored at the date of last disease assessment. Data for subjects who receive non-protocol specified T-PLL therapy (i.e., excluding stem cell transplantation for eligible CR subjects) prior to disease progression will be censored at the last disease assessment prior to receiving non-protocol therapy. Data for subjects without any disease assessments performed after the baseline visit will be censored at the time of dosing plus 1 day. PFS

will be analyzed by Kaplan-Meier methodology. Median PFS will be calculated and 95% confidence interval for median PFS will be presented.

Duration of Response (DoR) will be defined as the number of days from the date of first response (CR, CRi, or PR) to the earliest date that progressive disease (PD) or death. For subjects who have a PR before CR, or CRi, in subsequent visits, the DoR is computed from the earliest PR. If the subject has not experienced disease progression or death, the subject's data will be censored at the date of last disease assessment. For subjects who do not have subsequent disease assessment after their first response, the subject data will be censored at the first response. For subjects who never experience response, the subject's data will not be included in the analysis. DoR will be analyzed by Kaplan-Meier methodology. Median DoR will be calculated and the corresponding 95% confidence interval will be presented.

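### SAP 6.4's transplant proportion is 100% by definition, and the documents conflict on progression assessment after transplant; if it stops, duration-of-response censoring depends on later outcome

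*Protocol*

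**What the plan says.** **Transplant endpoint.** Protocol 3.3 and SAP 4.3.2 make the endpoint a number. Both define eligible subjects as transplant-naïve subjects who achieved CR. SAP 6.4 turns it into a proportion of eligible subjects and adds to the definition of eligible that they then went on to transplant.

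**Follow-up after transplant in CR.**
- Synopsis, with the same words in Protocol 4.1: "combination therapy will be discontinued but subjects will be followed for disease progression".
- Operations Manual 3.14, for any subject without PD at permanent discontinuation: "Disease assessment will continue to be performed after the last dose of study drug until disease progression".
- Operations Manual 2.2: "Post-treatment follow-up visits will be conducted until documented progressive disease (PD) or other post-treatment therapies (including stem cell transplantation) are received". Section 3.11 has the same stop, "until documented PD or other post-treatment therapies (including stem cell transplantation) are received", as does a footnote to Table 5 in 3.17.
- Once those visits end, Operations Manual 2.2 says that subjects "should be contacted every 6 months by telephone for survival assessment and for information on new anticancer therapies". Section 3.11 adds cause of death and post-study treatment with reasons, regimens and dates.
- Protocol 5.6 keeps subjects who discontinue drug prematurely on all regularly scheduled visits.

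**Analysis rules (SAP 6.3).**
- DoR runs to PD or death. Otherwise it is censored at the last disease assessment. It has no rule for transplant or new therapy.
- PFS is censored before non-protocol therapy, at the last assessment that precedes it. Planned transplant is exempt from that rule: "i.e., excluding stem cell transplantation for eligible CR subjects".
- EFS counts new anti-T-PLL therapy as an event. Without an event it is censored at the last assessment or at the transplant date. The SAP does not say whether transplant in CR is new therapy, or which date applies to whom.

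**The concern.** A proportion whose denominator contains only subjects already in the numerator says nothing about how many subjects in CR reach transplant, which is the secondary objective.

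The follow-up conflict matters because transplant after CR is the planned route for eligible subjects, so those affected are among the best responders. The visits that end at transplant are the ones that carry the response assessment. If they end, a death still reaches the database through the survival calls, but continued remission does not. The SAP rule then keeps those who die at risk until death and removes those who live from the risk set at an earlier date. Kaplan-Meier estimation assumes that censoring does not depend on prognosis, and here it would. DoR is most exposed because only responders enter it and any new therapy, not only transplant, triggers the problem. Assessments not made after transplant cannot be made later.

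**Working it through.** The documents give no expected transplant rate and no DoR, PFS or EFS figure, so there is no stated result to reproduce.

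**1. Transplant proportion.** Let c be the number of transplant-naïve subjects with CR, and k the number of them transplanted.
- Protocol 3.3 population: k/c.
- SAP 6.4 population: k/k = 100% for k ≥ 1, and 0/0 for k = 0.
- Illustration with c = 8 and k = 3: 3/8 = 37.5% against 3/3 = 100%. The count is 3 under both.

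**2. SAP 6.3 applied to subjects without recorded PD, if visits stop**

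| Endpoint | Dies later | Stays alive | Depends on outcome? |
|---|---|---|---|
| DoR, transplant or other new therapy | Event at death | Censored at last earlier assessment | Yes |
| PFS, transplant in eligible CR | Event at death | Censored at last assessment before transplant | Yes, unless recorded later non-protocol therapy triggers censoring |
| PFS, other new therapy | Censored before the therapy | Censored before the therapy | No |
| EFS, transplant not an event | Event at death, or at earlier new therapy | Censored at last assessment or at transplant | Yes |
| EFS, transplant an event | Event at transplant | Event at transplant | No |

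TTP does not have this mechanism because death is not an event, although it loses progressions after transplant. ORR, OS and the transplant count do not use these rules. If assessment continues to progression, the DoR and PFS rules are coherent for transplanted subjects.

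**3. Worked example (assumed data).** Ten CR subjects are transplanted 4 months after first response. Three die without progression at months 10, 14 and 20, and seven are alive at month 24.
- Full follow-up: 9/10 = 0.90, 8/10 = 0.80, 7/10 = 0.70; median not reached.
- SAP DoR rule with visits stopped: the seven survivors leave at month 4, so three remain at risk. The curve is 2/3 = 0.667, then 1/3 = 0.333, then 0; median 14 months.

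**4. Size in a trial like this one (simulation; every rate assumed).**
- 15 responders (37 × 0.40 = 14.8), with response at month 1. Untransplanted responders have exponential DoR with median 5 months.
- 3, 5 or 8 responders are transplanted at month 5, with last assessment at month 4.5.
- Relapse/non-relapse death after transplant is 2%/1%, 4%/2% or 6%/3% per month. Median time from relapse to death is 3, 6 or 12 months. Data cut is at month 30.
- This gives 27 scenarios. *As collected* means an event at death if dead by the cut, otherwise censored at month 4.5, with no relapse ever recorded.

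| Transplanted | Full follow-up, median DoR (months) | As collected | Shift |
|---|---|---|---|
| 3 of 15 | 6.2-6.7 | 6.1-6.5 | -0.6 to +0.3 |
| 5 of 15 | 7.1-8.4 | 7.0-7.7 | -1.4 to +0.6 |
| 8 of 15 | 8.5-12.4 | 8.9-9.8 | -3.5 to +1.2 |

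The shift is negative at the low event rates and positive at the high ones. Median PFS moves by less than 0.02 month throughout, largely because 37 - 15 = 22 subjects are non-responders. Choosing one EFS censoring date or the other, 0.5 month apart here, moves 18-month EFS by at most about 0.2 percentage points.

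**5. Uniform censoring as a fallback.** Censoring every transplanted subject at the last assessment before transplant removes the dependence on outcome. With 5 transplanted, however, its median DoR is 6.3-6.4 months, against 7.1-8.4 with full follow-up and 7.0-7.7 as collected. On the median it lies further from full follow-up than the current rule in all 27 scenarios.

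The ranking depends on the measure and the assumptions. A second, large-sample simulation assumed 20-60% of responders transplanted 4 months after response, an untransplanted median of 8 months, post-transplant medians of 12-24 months to progression and 18-36 months to death without progression, and 6 months from progression to death. There, uniform censoring was closer to full follow-up at 23 months in all 12 scenarios (for example 0.243 full, 0.159 uniform, 0.120 as collected).

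**The case against.** The strongest reply is that the problem is conditional. If the synopsis, Protocol 4.1 and Operations Manual 3.14 govern, transplanted subjects are assessed to progression and the PFS and DoR rules work. That is correct, but the visit sections say otherwise and describe no other visit at which progression after transplant would be assessed.

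A reader might infer that nothing about relapse is known after transplant. The documents do not support that. Operations Manual 3.11 collects cause of death and the reasons and dates of post-study treatment, which may reveal some relapses, although these are not scheduled disease assessments. The simulation records no relapse at all and is a worst case on that point. Protocol 5.6 might also keep visits going, but whether a planned transplant is premature discontinuation is arguable.

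A reader might also infer that DoR will be biased in a known direction, or that the primary result is at risk. Neither follows. The sign changes with the assumed rates, and the largest shift needs 8 of 15 responders transplanted, which nothing in the documents supports. These are secondary endpoints in a study that SAP 4.6 calls hypothesis generating. SAP 6.4 already allows a transplant-censored analysis, though only as an option.

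The ordinary reading of the EFS sentence is transplant date for transplanted subjects and last assessment for the rest. That is plausible but unstated. The SAP 6.4 denominator may be a drafting slip, since SAP 4.3.2 has the usable population. It is still wrong as written.

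**Conclusion.** Two points stand. First, the SAP 6.4 proportion is uninformative by construction and contradicts Protocol 3.3 and SAP 4.3.2. This needs no assumption.

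Second, current passages contradict each other on progression assessment after transplant. If assessment stops, DoR censoring depends on later outcome for any responder who is transplanted or starts other new therapy without recorded PD. PFS shares this only for transplant in eligible CR subjects, and EFS only so far as transplant is not itself an event.

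The size and direction of any bias cannot be fixed from the documents. With a fifth to a third of 15 responders transplanted, the assumed rates give shifts in median DoR between -1.4 and +0.6 month. The change should be made, but it does not bear on the primary conclusion.

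**What to change.** 1. **SAP 6.4.** Delete the closing clause of the definition of eligible subjects, which requires that they went on to transplant. The denominator becomes transplant-naïve subjects with CR, and the count is unchanged. There is no cost.
2. **Follow-up.** Reconcile the synopsis, Protocol 4.1, Protocol 5.6 and Operations Manual 2.2, 3.11, 3.14 and Table 5 to one rule on progression assessment after transplant. Which rule is for the sponsor to decide.
3. **SAP 6.3.**
   - If assessment continues, count progression and death after transplant.
   - If it stops, censor DoR and PFS at the last assessment before transplant regardless of later death, and do the same in DoR for any other new therapy. Report this as a different estimand (response duration before transplant or new therapy). State that in median DoR, under the first set of rates assumed above, it lies further from full follow-up than the current rule.
   - For EFS, say whether transplant in CR is an event. If not, name the censoring date for transplanted subjects and keep the last disease assessment for the others.

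The Operations Manual is Appendix I of the protocol, so item 2 is an amendment needing ethics committee approval under Protocol 8.1. Continued assessment also means collecting data after transplant. The SAP was written for the protocol dated 2 May 2019, whereas the current synopsis is dated 11 November 2020. SAP 3.0 already provides for an update when a protocol change affects the analysis.
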